- e Full physical examination: general appearance, head, eyes, ears, nose, and throat (HEENT), heart, chest, abdomen, skin, lymph nodes, extremities, musculoskeletal, and neurological systems. Brief physical examination: general appearance, HEENT, heart, chest, abdomen, and skin.
- f Vital signs include blood pressure, heart rate, respiration, and oral temperature.
- g Safety laboratory assessments include chemistry, hematology, coagulation, and urinalysis.
- h Patients who were previously treated with drisapersen will be tested for anti-platelet antibodies at Screening, and must have a normal platelet count prior to Week 1.
- i Samples obtained at Week 1 are considered Baseline for the untreated control group.
- The 6MWT and NSAA will be performed on 2 consecutive days and may require 2-night overnight stays. Pulse will be obtained prior to and immediately after the 6MWT.

CCI

1 ECG and ECHO may be performed on either day of the specified 2-day visits during the treatment period.

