5.3. Safety Set

The Safety Set will consist of all patients who are enrolled in the study and either receive at least 1 dose of eteplirsen in the eteplirsen-treated group or have at least 1 post-Baseline safety assessment in the untreated control group.

For patients in the untreated control group, any safety assessment (including AE assessment) on or after the Week 1 visit, will be considered a post-Baseline safety assessment.

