6.2.3 Handling of Incomplete Dates

An incomplete date will occur when the exact date an event occurred or ended cannot be obtained for a patient. Incomplete dates will be imputed as follows:

- For a partial or missing medication date, the medication will be classified as a concomitant medication unless the available part of the date indicates it is impossible for the drug to be concomitant. For example, if only the year for the stop date is available and the year is prior to the year of dosing, the medication will be classified as a prior medication.
- For a partial or missing AE onset date, the event will be classified as treatment emergent if the month and/or year of the onset date are on or after the initiation of eteplirsen and within 28 days of the last dose of eteplirsen for treated patients, or if the month and/or year of the onset date are on or after the date of the qualifying visit for untreated control patients.
- For the purpose of calculating the time since DMD diagnosis or duration of prior corticosteroid use, if the date of DMD diagnosis or the start date of corticosteroid use has a missing day but known month and year, then the 15th of the month will be used in the calculation. If only the year is known, December 31st of the recorded year will be used.

In all cases, the original missing or incomplete dates will be presented in the data listings.

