6.7. Definitions and Terminology

Day 1

Day 1 will be defined as the date of the first eteplirsen dosing for eteplirsen-treated patients, or the Week 1 visit date for untreated control patients.

Study Day

Study day will be defined as Event Date – Day 1 + 1.

Duration on Study

Duration on study will be calculated as the duration in weeks from Day 1 to the date of study completion/discontinuation as recorded on the END OF STUDY eCRF (if completed) or the date of the last study assessment or procedure.

Duration on Eteplirsen

Duration on eteplirsen will be calculated as the duration in weeks from Day 1 to the date of the last eteplirsen administration as recorded on the STUDY DRUG ADMINISTRATION eCRF plus 6 days (ie, [last dose – first dose date + 1 + 6]/7).

Duration in weeks calculated above will be then categorized to 1 of the following intervals: <24, 24 to <48, 48 to <72, 72 to <96, or ≥ 96 .

Planned Dose and Overdose

The body weight-based planned dose was calculated based on most recent weight of previous visits. When calculating the planned dose, the body weight is rounded to a single decimal using conventional rounding rules. While in preparing actual dose, an unconventional rule is applied for calculating the volume of the concentrated drug (50 mg/mL) in milliliter. Any volume of 0.1 or above is rounded up (eg 25.14 mL is rounded up to 26 mL) and any volume below 0.1 is rounded down (eg 25.09 mL is round up to 25 mL). The overdose is defined as any actual dose $>10\%$ above the planned body weight-based dose.

Baseline Visit and Baseline value

Baseline visit will be considered the last visit prior to the initiation of eteplirsen for eteplirsen-treated patients, or the last visit on or before the Week 1 visit for untreated control patients. For any assessment that is taken on 2 consecutive days at baseline visit the base visit (ie, 6MWT, NSAA items and total score, FVC % predicted), the average value will be considered as the baseline value. If the assessment is taken or available only on 1 day at baseline visit, then the value on that day will be used as baseline value.

Change from Baseline

Change from Baseline will be calculated as follows:

$$\text{Change from Baseline} = \text{Post-Baseline Value} - \text{Baseline Value}$$

Percent Change from Baseline

Percent change from Baseline will be calculated as follows:

$$\text{Percent change from Baseline} = (\text{Change from Baseline} / \text{Baseline Value}) * 100$$

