Treatment-emergent Adverse Event

An AE will be considered treatment-emergent if it occurs in the time period starting with the initiation of the first dose of eteplirsen and ending 28 days after the last dose of eteplirsen for eteplirsen-treated patients, or on or after the Week 1 visit date for untreated control patients.

To define treatment emergence for AEs with missing onset or stop date or time, the following additional criteria will be used:

If both start and stop dates for a particular AE are missing, then the AE is considered treatment emergent.

- If onset date for a particular AE is missing, and stop dates falls after the first date/time, then that AE is considered treatment emergent.

- If onset date for a particular AE is the same as the first dose date and the start times missing, and stop dates falls after the first date/time, then that AE is considered treatment emergent.

Treatment-related Adverse Event

A treatment-related AE is any AE reported on the ADVERSE EVENTS eCRF that is marked as definitely related, or probably/possibly related to study drug.

Treatment-emergent Laboratory Abnormality

A treatment-emergent laboratory abnormality will be defined as any laboratory abnormality occurring or worsening after the initiation of eteplirsen dosing and within 28 days of the last dose of eteplirsen for eteplirsen-treated patients or occurring or worsening on or after the Week 1 visit for untreated control patients.

Prior Medication

A prior medication will be any medication taken and completed prior to the first dose of eteplirsen for eteplirsen-treated patients, or before the Week 1 visit for untreated control patients.

Concomitant Medication

A concomitant medication will be any medication that is taken in the time period starting with the initiation of the first dose of eteplirsen dosing and ending 28 days after the last dose of eteplirsen for eteplirsen-treated patients, or on or after the Week 1 visit for untreated control patients.

Previous Drisapersen Exposure Status

A patient will be considered as having previous exposure to drisapersen if he had taken any drisapersen prior to Day 1 in this study (value=Yes); otherwise a patient will be considered as not having a previous exposure to drisapersen (value=No).

Time Since DMD Diagnosis

The time since DMD diagnosis, in months, will be calculated as (Day 1 – Date of DMD diagnosis + 1)/30.4375.

Duration of Corticosteroid Treatment

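### For untreated controls the Week 1 laboratory sample is both Baseline and inside the treatment-emergent window, and their AE start date is given two ways; the effect is small and its net direction uncertain

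*SAP*

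**What the plan says.** **Baseline.** Protocol Section 2, Table 5, footnote i: "Samples obtained at Week 1 are considered Baseline for the untreated control group". Table 5 schedules control safety laboratory tests at Screening and Week 1, with none at the Baseline visit between them. SAP 6.7 agrees, placing the control Baseline visit at "the last visit on or before the Week 1 visit for untreated control patients". For the treated group, "Baseline visit will be considered the last visit prior to the initiation of eteplirsen for eteplirsen-treated patients".

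**Laboratory window.** SAP 6.7 opens the control window inclusively: "occurring or worsening on or after the Week 1 visit for untreated control patients". For treated patients the definition covers "any laboratory abnormality occurring or worsening after the initiation of eteplirsen dosing and within 28 days of the last dose of eteplirsen". Protocol 10.2 requires assessments on an infusion day to be finished before the infusion begins, apart from post-dose PK draws.

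**Post-Baseline.** The Safety Set definition (SAP 5.3) says that for controls "any safety assessment (including AE assessment) on or after the Week 1 visit, will be considered a post-Baseline safety assessment".

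**Adverse events.** SAP 6.7 starts the control treatment-emergent period at the Week 1 visit date. SAP 6.2.3 classifies a partly dated control event as emergent if its onset month or year is "on or after the date of the qualifying visit for untreated control patients". For treated boys both sections start at the first dose.

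**Tables.** SAP 7.9.2 tabulates abnormalities arising after baseline, and the highest or lowest post-baseline values. It does not mention the treatment-emergent laboratory definition.

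**The concern.** A sample cannot be both the reference value and a follow-up value. As SAP 6.7 stands, an abnormality already present in a control at Week 1 can meet the emergent definition on the Baseline sample itself. The same pre-dose finding in a treated boy cannot. Safety results are shown side by side by treatment group, so the rule for what counts should be the same in each.

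SAP 7.9.2 does not remove the ambiguity, because it never says what after baseline means for a control. The only SAP text that calls particular control safety assessments post-Baseline is the sentence in 5.3, and it includes Week 1. Two programmers could therefore reach different control counts. The worst-value summaries share the problem: if Week 1 enters the control maximum, the change from Baseline to the highest value can never be negative in a control, whereas it can be in a treated boy.

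The adverse-event conflict is separate. Two control events with the same true onset could be classified differently only because one has an incomplete date.

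**Working it through.** The plan gives no figure on this point, so there is nothing to reproduce. The check is a count of samples followed by an illustration.

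**1. Countable laboratory samples through Week 96**

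- Controls (Protocol Table 5): Weeks 1, 4, 8, 12, 24, 36, 48, 72 and 96. The inclusive window counts 9, of which one is Baseline.
- Treated (Protocol Tables 2 and 3): Week 1 is pre-dose and excluded. Weeks 4, 8, 12, 24, 36, 48, 72 and 96 give 8.
- If the control window opened after the Week 1 sample, both groups would have 8.

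**2. Which criteria the extra sample can meet** (SAP Appendix Tables 1 to 3)

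- Criteria relative to Baseline (AST, ALT, LDH or CK at least 2 × Baseline; BUN above 1.5 × Baseline and above ULN) cannot be met by a sample that is itself the Baseline.
- Absolute criteria can be met: for example cystatin C above ULN, haemoglobin below LLN, urine protein above 1+.

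**3. Size for an absolute criterion**

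Let q be the chance that any one sample is flagged. The documents give no value, so I assume 2% to 10%, with samples independent.

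P(at least one flag in k samples) = 1 − (1 − q)^k

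Excess from the extra sample = q(1 − q)^8

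| q (assumed) | 8 samples | 9 samples | Excess (points) |
|---|---|---|---|
| 2% | 14.9% | 16.6% | 1.7 |
| 5% | 33.7% | 37.0% | 3.3 |
| 10% | 57.0% | 61.3% | 4.3 |

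With the planned 20 + 10 = 30 controls, this is 30 × 0.017 = 0.5 to 30 × 0.043 = 1.3 boys per criterion. These figures assume full follow-up. For a control with only k follow-up samples the excess is q(1 − q)^k, which never exceeds q.

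**4. What pulls the other way**

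Treated boys who go through the whole safety extension have further draws at Weeks 120, 144 and 148 (Protocol Table 4), so up to 8 + 3 = 11 post-dose samples. At the same q, 1 − (1 − q)^11 is 19.9%, 43.1% and 68.6%. Each exceeds the 9-sample control figure of 16.6%, 37.0% and 61.3%.

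**5. Adverse-event start dates**

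Eligibility is confirmed at the Baseline visit and reconfirmed at Week 1 (Protocol Table 5, footnote d), and Week 1 should fall within 4 weeks of Baseline (footnote c). The qualifying visit in SAP 6.2.3 may therefore precede the SAP 6.7 start by anything from nothing to about 4 weeks.

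**The case against.** The strongest reply is that the disputed laboratory definition may never be used. SAP 7.9.2 is where the laboratory tables are specified, and it does not invoke that definition. With Week 1 as the control Baseline, its natural meaning leaves that sample out. The sentence in 5.3 sits in a population definition and is most naturally read as governing membership only. This stands as a limit on the effect. It does not show that the wording is settled, because 7.9.2 never defines its own term.

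A reader might go further and infer that control rates absorb baseline prevalence while treated rates do not. With assumed prevalence p of 10% to 20% and new-onset rate q of 10%, p + (1 − p)q gives 0.10 + 0.90 × 0.10 = 19% to 0.20 + 0.80 × 0.10 = 28% in controls, against 10% in treated boys. The documents do not support that contrast, because it reads the undefined word occurring differently in each group. If it means newly arising, a Baseline value is neither new nor worse and controls gain nothing. If it means present, a treated boy's persistent abnormality counts from Week 4 too, and the groups differ only for Week 1 abnormalities that later resolve.

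Nor do the documents show that the tables favour eteplirsen. The extension draws act in the opposite direction, as does the large control dropout that SAP 4.4.2 reports, because it reduces the control samples available to be flagged.

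On adverse events, Protocol 11.2.1 already excludes findings present at Baseline unless they recur or worsen. The treated partial-date rule works on month or year, so it can also capture a pre-dose event in the month of first dosing. The qualifying-visit start has a source: Protocol 13.10.2.1 summarises control events collected after qualification. These points reduce the consequence, but SAP 6.2.3 and 6.7 still disagree.

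**Conclusion.** The plan is inconsistent as written in two places: the control Week 1 laboratory sample is both Baseline and eligible as emergent, and control adverse events have two start dates. The treated group has neither problem.

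The laboratory consequence is minor: one extra countable sample, worth about 2 to 4 percentage points per absolute-threshold criterion. That rests on assumed per-sample rates of 2% to 10%, independence, full follow-up to Week 96, and the 6.7 or 5.3 wording being applied to the 7.9.2 tables. The net direction of any whole table is uncertain. The partial-date effect cannot be sized from the documents. The safety summaries are descriptive and SAP 8.1 rules out inference between these groups, so no test or power is affected. This is a drafting correction worth making, not evidence of a biased safety comparison.

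**What to change.** - **SAP 6.7, laboratory definition:** start the control window after the Week 1 Baseline sample, and define occurring as absent at Baseline, in both groups.
- **SAP 7.9.2:** state that after baseline (and post-baseline) excludes the control Week 1 sample.
- **SAP 6.2.3:** replace the qualifying visit with the Week 1 visit date, to match 6.7. Protocol 13.10.2.1 uses qualification as the start, so note the choice among the changes from the protocol in SAP 8.1.
- **SAP 5.3:** leave membership unchanged, and add that its post-Baseline wording applies to set membership only. Requiring a later assessment would impose a follow-up condition on controls alone, since treated boys enter on their first dose, and could remove controls who leave early.

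The cost is a few sentences of SAP text and the matching programming specification. No new data are needed and no patient leaves an analysis set.

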6.2. Handling of Missing Data

6.2.1 Imputation of Missing Values

6WMT distance

If the patient is confirmed to have LOA (section 6.7), a value of 0 (zero) meters will be imputed for any missing values at the time or after the confirmation of LOA.

CCI

NSAA item and total score

If 4 or fewer of 17 NSAA items are missing, the score for the missing items will be assigned a value of zero. The NSAA total score will be calculated as the sum of the scores for the completed items. The total NSAA score will be treated as missing values when 5 or more items are missing.

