The duration of corticosteroid treatment, in months, will be calculated as (Day 1 – Date on which the patient started corticosteroid treatment + 1)/30.4375.

Corticosteroid Schedule

Corticosteroid schedules will include:

- Continuous (daily)
- Intermittent (includes all dosing schedules that do not require the patient to take at least one dose per day)

Non-Ambulatory Status and Loss of Ambulation (LOA)

The non-ambulatory status will be considered as “Yes” if all 3 conditions below are met:

- NSAA walk subscore as “0” (unable to achieve goal independently) on 2 consecutive days within a visit or NSAA was not done due to reason related to non-ambulation
- 6-minute walk test was not done with any reason related to permanent non-ambulation
- No later data showing this patient is still ambulatory. This is not required if non-ambulatory status occurs at the time of early withdrawal, or at the end of Week 96 assessment.

Note, when the NSAA or 6MWT is “Not Done” and the patient meets the non-ambulatory requirements above, a query will be issued to sites to confirm the permanence of non-ambulatory status. Prior to final database lock, the results of queries will be reviewed by Medical Director and Data Management and provided as documentation for non-ambulatory status determination.

Time to LOA is defined as the time from the initiation of eteplirsen for eteplirsen-treated patients, or Week 1 visit for untreated control patients to the first time of permanent non-ambulation. Patients who do not lose ambulation at the time of early withdrawal, or at the end of Week 96 assessment, whichever is earlier, the patient will be censored at the last time at which the patient is determined to be ambulatory.

NSAA and Total Score

The NSAA is a clinician-administered scale specifically designed for DMD patients that rates patient performance on various functional activities. Patients will be asked to perform 17 different functional activities including: stand, walk, stand up from chair, stand on one leg - right, stand on one leg - left, climb box step - right, climb box step - left, descend box step - right, descend box step - left, lift head, get to standing, rise from floor, stand on heels, jump, hop right leg, hop left leg, run 10 meters. Patients will be graded as follows

- 2 = achieves goal without any assistance;
- 1 = modified method but achieves goal independent of physical assistance from another person; and
- 0 = unable to achieve goal independently.

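### The loss-of-ambulation rule accepts only a 6MWT that was not done, so a visit with a failed attempt is not an event: LOA is delayed, or lost if no qualifying visit follows

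*SAP*

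**What the plan says.** The protocol leaves the definition of LOA to the SAP (Protocol 13.9.1.2) and says that LOA is measured with the 6MWT (Protocol 7.4.3).

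SAP 6.7 classes a boy as non-ambulatory "if all 3 conditions below are met":

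- **Condition 1 (NSAA)** has two routes. The walk subscore is 0 "on 2 consecutive days within a visit or NSAA was not done due to reason related to non-ambulation".
- **Condition 2 (6MWT)** has one route: "6-minute walk test was not done with any reason related to permanent non-ambulation".
- **Condition 3 (persistence)** is "No later data showing this patient is still ambulatory". It is waived at early withdrawal and at the end of Week 96.

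The site check is tied to the same rule. When the NSAA or 6MWT is recorded as not done and "the patient meets the non-ambulatory requirements above, a query will be issued to sites to confirm the permanence of non-ambulatory status". Time to LOA runs "to the first time of permanent non-ambulation". A boy without an event is censored at the last time he was judged ambulatory.

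Two other rules interact with this one. SAP 6.2.1 says that once LOA is confirmed, "a value of 0 (zero) meters will be imputed for any missing values at the time or after the confirmation of LOA". SAP 7.8 treats an efficacy value flagged on the eCRF as invalid or unsuccessful as missing.

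**The concern.** A boy can score 0 on the NSAA walk item on both days and still be asked to try the 6MWT. If he tries and cannot walk, the test was attempted, so condition 2 is not met at that visit. Whether the visit counts as LOA then depends on how the attempt was entered, not on his function.

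LOA is a secondary endpoint, and it also controls the 0 m imputation in the primary endpoint. A visit that the rule does not recognise can therefore make time to LOA look longer. On one recording branch, it can also remove a very poor walk from the Week 96 6MWT summary. Both effects make outcomes look better than they were.

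**Working it through.** The documents state no LOA rate, event count or power for LOA, so there is no planned figure to reproduce. The check has four steps.

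**1. The rule as a truth table.** Take NSAA walk 0 on both days, so that condition 1 is met.

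| 6MWT at this visit | Later data | LOA event at this visit? |
|---|---|---|
| Not done, permanent non-ambulation | None, or last visit | Yes |
| Not done, permanent non-ambulation | Later 6MWT also not done | Yes |
| Not done, permanent non-ambulation | Later ambulatory | No |
| Attempted, 0 m or not completed | None, or last visit | **No** |
| Attempted, 0 m or not completed | Later 6MWT not done | **No; event dated to the later visit if the other conditions hold there** |
| Attempted, 0 m or not completed | Later ambulatory | No |

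The fourth row loses the event and the fifth delays it.

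**2. Whether another rule closes the gap.**

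- The query does not. It needs a test recorded as not done and a boy who already meets the requirements. Here the NSAA was scored and the 6MWT was attempted.
- SAP 7.8 does not. It makes an unsuccessful value missing, but nowhere is that status equated with not done.
- The parallel rule in SAP 6.7 for loss of the ability to rise accepts either a subscore of 0 on both days or an NSAA missing because the boy could not do the task. LOA condition 2 has no failed-attempt route.

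**3. Size for LOA.** The input is about 70 treated boys with Baseline 300–450 m (SAP 4.2). One lost event changes the crude proportion by 1/70 = 1.43 percentage points.

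A Kaplan-Meier illustration uses *assumed* true events: 2 at Week 48, 4 at Week 72 and 4 at Week 96, with no other censoring before Week 96.

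- All events counted: 60/70 = 85.7% ambulatory at Week 96.
- With k of the Week 96 events lost and censored at Week 72: (64/70) × 60/(64 − k). For k = 1, 2, 3, 4 this gives 87.1%, 88.5%, 89.9% and 91.4%.
- With 1 to 4 events delayed from Week 72 to Week 96: the Week 72 estimate rises from 64/70 = 91.4% to between 65/70 = 92.9% and 68/70 = 97.1%. Week 96 stays at 85.7%.

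**4. Size for the 6MWT mean.** This applies only if the failed attempt is set to missing under SAP 7.8 and LOA is not confirmed. Let n other boys have mean change m, and let the missed boy have Baseline b, so that his change with 0 m would be −b. Including him shifts the mean by

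(n·m − b)/(n + 1) − m = −(b + m)/(n + 1).

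The range b = 300 to 450 m is that of the primary efficacy set. The values n = 50 to 60 and m = −50 to −110 m are assumptions.

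- Smallest shift: b = 300, m = −110, n = 60 gives −190/61 = −3.1 m.
- Largest shift: b = 450, m = −50, n = 50 gives −400/51 = −7.8 m.

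Leaving him out therefore makes the mean change look about 3 to 8 m better per boy. If the attempt is recorded as a valid 0 m, the value is already in the mean and the shift is zero.

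**The case against.** The strongest reply is that the gap may never arise. How a failed attempt is entered depends on the eCRF and the Clinical Evaluator Manual, which are not in the public documents. Condition 2 refers to a reason for the test not being done, so a site could naturally enter the test as not done because the boy could not walk. The rule would then work. This stands as a limit on frequency, but it does not settle the wording: the SAP uses separate terms for a test that was not done and one that was not completed successfully, and never links them.

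A reader might infer that such a boy can never become an LOA event, or that all his later missing walks stay missing. The documents do not support either. At a later attended visit where the 6MWT is not done because he can no longer walk, all three conditions can be met, and SAP 6.2.1 then imputes 0 m from that point. Nor is he censored at the failed visit: censoring is at the earlier time when he was last judged ambulatory.

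It is also fair to say that little inference rests on LOA. SAP 7.8.2 plans descriptive Kaplan-Meier summaries, SAP 8.1 removes every test between the two groups, and the same rule applies to both. No alpha or power is affected. But a descriptive estimate still carries any misclassification directly. SAP 4.4.2 plans to evaluate the treatment effect against external controls under a supplemental SAP that is not available here, so whether this LOA rule enters that comparison is unknown.

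**Conclusion.** The gap in the definition is real. Followed literally, a visit with NSAA walk 0 on both days and a failed 6MWT attempt is not an LOA event. The event is delayed to the first later visit that qualifies, or lost if none follows, as at Week 96 or early withdrawal. Any error is towards fewer or later events.

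The size is about 1.4 percentage points per lost event among 70 boys. On the missing-value branch alone, it is about 3 to 8 m per boy in the Week 96 mean change, given the assumed n and mean decline.

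A reader might infer that the reported LOA estimates are shown to be biased. That goes too far: the number of such visits cannot be derived from the documents and could be zero. The point is worth correcting because the rule gives the wrong answer for a foreseeable case and the correction is cheap.

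**What to change.** - **Condition 2.** Reword it so that it is met when the 6MWT was not done, or was attempted with 0 m recorded or not completed successfully, in each case for a reason related to permanent non-ambulation.
- **Imputation.** Apply the same rule in SAP 6.2.1, so that a failed attempt set to missing under SAP 7.8 becomes 0 m once LOA is confirmed.
- **Query.** Send the permanence query for every visit with an NSAA walk subscore of 0 on both days, not only when all conditions are already met.
- **Last visits.** Require confirmation from that query at Week 96 and at early withdrawal. Condition 3 is waived there, so it cannot protect against false events at the visits where true events would otherwise be lost.

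The cost is one SAP clause and a few more site queries before database lock.

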9.6. Blinding and Randomization

This is an open-label study, and therefore patients and Investigators will be aware of the patient's treatment. However, to minimize assessment bias, every effort will be made to keep the clinical evaluators unaware of the treatment group of the patients, and all biological efficacy endpoint evaluations will be performed by blinded assessors.

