12.2. Quality Assurance

The CRFs will be reviewed at regular intervals by a clinical monitor from the Sponsor or a representative of the Sponsor per the agreed upon Monitoring Plan against the source documentation for identification and clarification of any discrepancies. Automated and manual quality checks will be in place to identify discrepancies, such as missing data, protocol deviations, out-of-range data, other data inconsistencies and compliance. Requests for data clarification or correction will be documented as electronic queries within the CRF and for the Investigator or study coordinator to resolve. All changes to the CRFs will be tracked in an electronic audit trail. Site Study Files will be reviewed for compliance throughout the study.

Audits may be carried out by the Sponsor's representatives, and inspections may be performed by IRBs/IECs or regulatory authorities before, during, or after the study. The Investigator will allow and assist the Sponsor's representatives and any regulatory agency to have direct access to all study records, CRFs, patient medical records and other source documentation, IP dispensing records and IP storage area, study facilities, and any other source documentation.

The Investigator must make study files and data accessible to the study monitor, to other authorized representatives of the Sponsor, and to the appropriate regulatory authority inspectors such as the United States Food and Drug Administration (US FDA).

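### The loss-of-ambulation permanence query reaches only boys already classed as non-ambulatory, so it can confirm or remove an event but cannot add one

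*SAP*

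**What the plan says.** Protocol 13.9.1.2 leaves the definition of LOA to the SAP. SAP 6.7 sets three conditions, all of which must hold:

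- The NSAA walk item is 0 on both days of a visit, or the NSAA was not done for a reason related to non-ambulation.
- The second condition concerns the walk test itself: "6-minute walk test was not done with any reason related to permanent non-ambulation".
- The third condition looks ahead in time: "No later data showing this patient is still ambulatory". On this third condition the SAP adds: "This is not required if non-ambulatory status occurs at the time of early withdrawal, or at the end of Week 96 assessment".

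A note then describes the check. When either test is marked as not done "and the patient meets the non-ambulatory requirements above, a query will be issued to sites to confirm the permanence of non-ambulatory status". Before final lock, "the results of queries will be reviewed by Medical Director and Data Management and provided as documentation for non-ambulatory status determination". The SAP does not say whether these reviewers see the treatment group.

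LOA status is used twice. It is a secondary endpoint, shown by group with Kaplan-Meier curves (SAP 7.8.2), in which a boy without LOA is censored when last known to be ambulatory. It also enters the primary endpoint through SAP 6.2.1: once LOA is confirmed, "a value of 0 (zero) meters will be imputed for any missing values at the time or after the confirmation of LOA". No other rule for filling in a missing 6MWT is visible.

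SAP 4.4.2, 6.3, 7.8 and 8.1 rule out a comparison of treated with untreated boys. SAP 4.4.2 sends the evaluation of effect to an external control, described in a supplemental SAP.

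**The concern.** A check on an endpoint should reach the uncertain cases. This one reaches only cases where the site has already recorded permanent non-ambulation as the reason for the missing walk test. The doubtful boy, who did not walk and whose recorded reason is vague, fails the second condition and so falls outside the query. The check is one-directional by construction.

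Two outputs are at stake. The LOA curve can lose or delay a true event. The Week 96 6MWT summary can lose a value of 0 m, which is the worst possible outcome, and an observed-case mean then looks better than it should.

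Two gaps in wording add to this. The reviewers are not said to be masked, and the later data that can cancel an event have no stated source.

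**Working it through.** **Who is queried.** Applying the three conditions and the note to possible records at a functional visit:

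| NSAA | 6MWT | Meets the conditions? | Queried? | Result |
|---|---|---|---|---|
| Walk 0 on both days, or not done for non-ambulation | Not done, permanent non-ambulation | Yes, if the third also holds or is waived | Yes | LOA kept or removed |
| Same | Not done, unclear or other reason | No (second fails) | No | Not LOA; 6MWT missing |
| Not done, unclear reason | Not done, permanent non-ambulation | No (first fails) | No | Not LOA; 6MWT missing |

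The second condition requires a 6MWT that was not done, so every boy who meets the definition is queried and nobody else is. The query has no path from not-LOA to LOA.

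**Effect on the Week 96 mean change.** The documents give no LOA rate or misclassification rate, so there is no figure of the plan's to reproduce. What follows is an illustration on assumed values.

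Let *n* other boys have mean change *m*, and let one LOA boy have Baseline *B*, so that his change is -*B* when 0 m is imputed.

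- With him: (*n*·*m* - *B*)/(*n* + 1). Without him: *m*. Shift: (*m* + *B*)/(*n* + 1).
- *n* = 60, *m* = -100 m, *B* = 375 m: (-6000 - 375)/61 = -104.5 m becomes -100 m, a shift of 275/61 = 4.5 m.
- *n* = 10, same values: 275/11 = 25.0 m.

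A second set of assumptions takes 70 treated boys (the planned number, SAP 4.2), Baseline 350 to 400 m, 7 to 14 true LOA cases, and -60 m in the others:

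- Low end (350 m, 14 cases): (14 × -350 + 56 × -60)/70 = -118.0 m. With one event lost, (13 × -350 + 56 × -60)/69 = -114.6 m. Shift 3.4 m.
- High end (400 m, 7 cases): (7 × -400 + 63 × -60)/70 = -94.0 m. With one event lost, (6 × -400 + 63 × -60)/69 = -89.6 m. Shift 4.4 m.
- Two events lost: 6.8 to 9.0 m.

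**Effect on LOA.** At the planned sizes, one event is 1/70 = 1.4 percentage points of the treated boys and 1/20 = 5.0 points of the controls, as crude proportions.

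**Later data.** Protocol Tables 2, 3 and 5 schedule the 6MWT and NSAA at Weeks 12, 24, 36, 48, 72 and 96 in both arms. After a Week 48 event there are two further functional visits in each arm. Treated boys also have weekly infusions, about 48 from there to Week 96, while controls have only the visits at Weeks 72 and 96. No walking test is scheduled at the infusion visits between functional visits. The two counts differ only if records other than the 6MWT and NSAA are accepted as later data, which the SAP neither states nor excludes. These counts do not enter the metre figures above.

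**The case against.** **Other cleaning could add events.** Protocol 12.2 states: "Automated and manual quality checks will be in place to identify discrepancies, such as missing data, protocol deviations, out-of-range data, other data inconsistencies and compliance". Protocol 12.1 adds full source verification. A general query could bring out a clear reason for a missed walk test, after which the boy would meet the definition. This stands: the one-way property belongs to the LOA query and not to data cleaning as a whole. These checks contain no permanence question, however, so they do not replace it.

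**Removing an event may be correct.** The endpoint is permanent loss, and a boy who later walks should not count. This also stands. The defect is that the doubtful boy on the other side of the line is not asked.

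**No between-arm test.** This limits the consequence within this SAP. It does not remove it, because the treated-arm curve and means are still reported and may be set against an external control.

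**A stronger reading that a reader might infer** is that events are overturned more easily in treated boys, who are seen weekly, so that the plan is biased in favour of eteplirsen. The documents do not support this. The later-data condition is waived at early withdrawal and at Week 96, so a boy found non-ambulatory then cannot be overturned by later records. If an earlier event is cancelled and he still cannot walk at Week 96, the event is re-dated and not lost. Functional tests follow the same schedule in both arms. A missed event in a control boy flatters the controls, and the control dropout that SAP 4.4.2 calls large leaves the net direction open.

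**Nor is it shown that the reviewers are unmasked.** Protocol 9.6 says "This is an open-label study, and therefore patients and Investigators will be aware of the patient's treatment", which covers the sites that answer the queries. SAP 4.4.2 places unblinding after lock. The masking of the reviewers is simply not stated, whereas Protocol 13.4 does specify a blinded review for deviations.

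**Conclusion.** The LOA query in SAP 6.7 can confirm or remove an event and cannot add one. A true LOA with an unclear reason for the missed 6MWT can be censored, and the walk distance left missing instead of set to 0 m.

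This can under-count LOA and improve the mean 6MWT change in whichever arm it happens. One missed event is worth about 4.5 m in a mean over 60 other boys, or 3.4 to 4.4 m under the second set of assumptions. It is worth more in a small group; the 25 m figure, with 10 others, suits the control arm, where it would work against eteplirsen. All of these rest on assumed Baselines, declines and event counts, and on the boy still being unrecognised as LOA at Week 96. If a clear reason is recorded at a later visit, his event is only dated late.

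The number of boys affected and the net direction between arms cannot be determined from the documents. The undefined later data are a secondary gap, which could favour treated boys only if non-functional weekly records were accepted. The point is worth correcting because LOA status decides who counts as 0 m in the primary endpoint, and the treated-arm results may be used in the external-control evaluation.

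**What to change.** In SAP 6.7, before database lock:

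1. In both arms, issue the ambulation-status query for every post-Baseline functional visit with the 6MWT not done, the NSAA not done, or an NSAA walk score of 0, whatever reason is recorded.
2. Have the answers reviewed on a listing without arm, genotype, dosing and biopsy fields, and record the decisions before arm is merged. SAP 6.8 sorts listings by treatment group by default, so this listing needs its own specification.
3. As a clarification, state that later data means 6MWT and NSAA results from functional visits through Week 96 or early termination.

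The first two changes can alter which boys count as LOA or as 0 m. The third mainly removes an ambiguity. The cost is SAP wording, a few more site queries and one masked listing, with no added patient procedures.
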